6.2.9 ECG

A standard 12-lead ECG will be performed using local standard procedures as defined in Study Assessments and Treatment Schedule *(Table 1)*. Additional ECGs will be obtained if clinically indicated. Triplicate ECGs will be performed to confirm the significant changes of single ECG. If ECG finding is considered as clinically significant, it should be recorded as medical history/adverse event appropriately. On the day of dosing, ECG will be performed prior to dose administration.

6.3 Eastern Cooperative Oncology Group (ECOG) Performance Status

ECOG performance status will be assessed as below at time points specified in the Schedule of Event.

Score	Description
0	Normal activity. Fully active, able to carry on all pre-disease performance without
	restriction.
1	Symptoms, but ambulatory. Restricted in physically strenuous activity, but
	ambulatory and able to carry out work of a light or sedentary nature (e.g., light
	housework, office work).
2	In bed < 50% of the time. Ambulatory and capable of all self-care, but unable to
	carry out any work activities. Up and about more than 50% of waking hours.
3	In bed > 50% of the time. Capable of only limited self-care, confined to bed or
	chair more than 50% of waking hours.
4	100% bedridden. Completely disabled. Cannot carry on any self-care. Totally
	confined to bed or chair.
5	Dead

6.4 Disease assessment

The disease assessment will be done by an expert haemato-oncologist/oncologist by evaluating disease-related symptoms/cytopenias, physical examination, lymph nodes assessment, assessment of organomegaly and constitutional symptoms. Based on the disease assessment, Rai staging will be

CONFIDENTIAL Page 35 of 61

Version: 1.0, Dated 12 September 2019

performed to define risk status of the patients (low risk disease, intermediate-risk disease and high-risk disease) [11].

Table 3:Rai staging system

Stage	Description	Modified Risk
		Status
0	Lymphocytosis, lymphocytes in blood >5 x 10 ⁹ /L clonal B-	Low
	cells and >40% lymphocytes in the bone marrow	
I	Stage 0 with enlarged node (s)	Intermediate
II	Stage 0-I with splenomegaly, hepatomegaly, or both	Intermediate
III	Stage 0-II with hemoglobin <11.0 g/dL or hematocrit <33%	High
IV ^c	Stage 0-III with platelets <100,000/μL	High

^C Immune-mediated cytopenias are not the basis for these stage definitions.

6.5 Radiological assessment

Initial disease assessment of relapsed/refractory CLL patient should be performed within 28 days prior to the first dose of study drug using CT scan of neck/chest/abdomen/pelvis, as applicable (This scan will be considered as baseline scan). The PI should review baseline scan images to confirm the subject has measurable disease as defined in the inclusion criteria. Scan performed as part of routine clinical management is acceptable for use as the baseline scan if it is of diagnostic quality and performed within 28 days prior to the C1D1 or as approved by the medical monitor if it is out of window period. Subsequently, CT scan should be done throughout the study at time-points designated in Study Assessments and Treatment Schedule (*Table 1*). Other radiological evaluations (e.g. MRI/USG) will be performed if warranted.

Disease response assessments should be performed at C3D1 (\pm 7 days), C5D1 (\pm 7 days) and C8D1 (\pm 7 days), and/ or at the EOT or as clinically indicated (if clinical progression is suspected). If CT scan at Screening is negative for disease involvement in the neck, subsequent CT scan may not include neck. If CT scan at Screening are positive for disease involvement of the neck, subsequent CT scan must include neck.

Note: Evaluation of radiological assessment will be performed and confirmed by the site investigator (defined as PI-confirmed response). The PI confirmed response will be considered for analyses of efficacy endpoints.

6.6 Bone marrow biopsy

Unilateral bone marrow aspiration and/or biopsy will be performed at investigator discretion in patients for whom assessment of extent of CLL involvement and bone marrow cellularity is important in determining eligibility during screening period (within 28 days prior to the first dose of study drug). However, bone marrow biopsy should be done to confirm potential CR.

To define a CR, the cytological or pathological evaluation of the bone marrow smear or biopsy must be at least normocellular for age, without evidence for typical CLL lymphocytes by morphological criteria.

CONFIDENTIAL Page 36 of 61

Version: 1.0, Dated 12 September 2019

Note: Bone marrow biopsy/aspirate will be performed at the site (local lab) as a diagnostic procedure as per the site practice.

6.7 Trial Treatment Period

Patients will visit the study center bi-weekly for the first two cycles and thereafter every month. All visits should occur as close as possible to the protocol specified time. Complete listings of the assessments that will be performed at each visit during the trial treatment period are specified in *Table 1*.

Trial treatment period is of 7 cycles (C1D1 to C8D1). Assessments will be performed thereafter if warranted, at the discretion of PI. Patients with progressive disease or unacceptable toxicity should be discontinued from the trial; patients with stable disease or response to therapy will continue treatment. The assessments to be performed are specified in Table 1.

6.8 End of Trial Treatment (EOT)

Patients are permitted to continue Tenalisib treatment until C8D1 unless there is disease progression, or discontinuation of patients due to unacceptable toxicity or decision to discontinue treatment by the patient (consent withdrawal)/PI. Follow-up evaluations required after treatment ends are specified in *Table 1*.

Treatment Beyond Cycle 8: Post C8D1, patient experiencing clinical benefit with no evident disease progression will be given the opportunity to enroll in an open-label compassionate medication use study and will be followed up.

All patients who discontinue Tenalisib will have an End of Treatment visit within 7 days from the last dose of the study drug. If treatment is discontinued because of toxicity or any other reason(s), the date of discontinuation will fulfill the End of Trial Treatment Visit. Patients who will be considered for compassionate use study protocol will have EOT assessment on C8D1.

6.9 End of Study (EOS)

All patients must be followed for adverse events for 30 calendar days after the last dose of study drug. Telephonic follow up is acceptable. Patients who will be considered for compassionate use study protocol will have EOS visit on C8D1. In case of drug related AEs, further safety assessments will be performed as warranted at the discretion of PI. The patient will be followed till resolution or stabilization of related adverse event.

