3.2 Design of Trial

The trial is a Phase II, open label, Simon's two stage study design to evaluate the efficacy and safety of Tenalisib in 61 patients with CLL who have relapsed or are refractory after at least one prior therapy. In Stage 1, 20 patients will be enrolled and the study treatment Tenalisib (800 mg BID) will be administered orally in 28-days of cycle over a period of 7 months (C1D1 to C8D1) in absence of definitive disease progression or unacceptable toxicity. If 8 or fewer responders are observed in this stage, the study will be terminated. Else, 41 additional patients will be enrolled into stage 2.

Patients will be evaluated for efficacy response by CT at C3D1±7 days, C5D1±7 days and C8D1±7 days and/or at End of the treatment (EOT) visit. The study will end when all ongoing subjects have reached their third tumor assessment on Cycle 8/Day 1 (C8D1) or have discontinued from the study for any reason, whichever is earlier. At the end of the study, all ongoing patients with no evident disease progression will be given the opportunity to enroll in an open-label compassionate medication use study [Protocol:RP6530-1803; NCT03711604] and will be followed up. The details of the study procedures are given in Study Assessments and Treatment Schedule (*Table 1*).

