6 TRIAL ASSESSMENT AND PROCEDURE

6.1 Overview

Schedule of Event summarizes the trial procedures to be performed at each visit and is divided into following.

- 1. Screening (Day -28 day to Day 0)
- 2. On treatment procedures (C1D1 to C8D1)
- 3. End of Treatment (Day +7 from last dose)
- 4. End of Study (Day +30 from last dose)

Individual trial procedures are described in detail below. It may be necessary to perform these procedures at unscheduled time points if deemed clinically necessary by the investigator.

Furthermore, additional evaluations/testing may be deemed necessary by the investigator and or the sponsor for reasons related to subject safety. In some cases, such evaluation/testing may be potentially sensitive in nature (e.g., HIV, HBV, HCV and CMV), and thus local regulations may require that additional informed consent be obtained from the subject. In these cases, such evaluations/testing will be performed in accordance with local regulations.

Protocol No. RP6530-1901 Rhizen Pharmaceuticals SA

Version: 1.0, Dated 12 September 2019

Table 1: Study Assessments and Treatment Schedule												
Day	Screening	C	C1	C	22	C3	C4	C5	C6	C7	C8/ EOT ¹⁸	EOS ¹⁹
Day		D 1	D15	D 1	D15	D 1	D1	D1	D1	D1	D1	-
Window period	-28	0	±1	±1	±1	±3	±3	±3	±3	±3	+7	+30
Study Days	D-28 to 0	1	15	29	43	57	85	113	141	169	197	227
Informed consent ¹	X	-	-	-	-	-	_	-	-	-	-	-
Demographics ²	X	-	-	-	-	-	-	-	-	-	-	-
Medical history ³	X	-	-	-	-	-	-	-	-	-	-	
Vitals ⁴	X	X	X	X	X	X	X	X	X	X	X	-
Height and weight ⁵	X	X	X	X	X	X	X	X	X	X	X	-
Complete physical exam ⁶	X	-	-	-	-	-	-	-	-	-	X	-
Abbreviated physical exam ⁶	-	X	X	X	X	X	X	X	X	X	-	-
ECOG Performance Status	X	X	_	-	_	X	_	X	_	_	X	-
Rai Staging	X	-	-	ı	-	ı	-	-	-	-	-	-
Laboratory assessment												
Complete blood count ⁷	X	X	X	X	X	X	X	X	X	X	X	-
Chemistry panel I ⁸	X	X	X	X	X	X	X	X	X	X	X	-
Chemistry panel II ⁹	X	X	-	-	-	X	-	X	-	-	X	-
Serology ¹⁰	X	-	-	-	-	-	-	_	-	-	-	
PT and INR ¹¹	X	X	X	X	X	X	X	X	X	X	X	_
Urinalysis (routine)	X	X	X	X	X	X	X	X	X	X	X	-
Pregnancy test ¹²	X	X	-	ı	-	ı	-	-	-	-	-	-
12-lead ECGs ¹³	X	X	-	X	-	X	-	X	-	-	X	-
Bone marrow biopsy/ aspirate ¹⁴	X	-	-	-	-	-	_	-	-	-	-	-

CONFIDENTIAL Page 29 of 61

Protocol No. RP6530-1901 Rhizen Pharmaceuticals SA

Version: 1.0, Dated 12 September 2019

Disease assessment												
Radiological scan/imaging ¹⁵	X	-	1	1	-	X	1	X	ı	1	X	-
Treatment administration												
Tenalisib treatment ¹⁶	-	X	X	X	X	X	X	X	X	X	X	-
Tenalisib dispensing	-	X	-	X	-	X	X	X	X	X	X	-

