- 19. Patients should be followed for AEs for 30 calendar days after the last dose of study drug. Telephonic follow up during this period is acceptable. All new AEs occurring during this period should be reported and followed until resolution unless, in the opinion of the investigator, the adverse event or laboratory abnormality/ies are not likely to improve because of the underlying disease.

CONFIDENTIAL Page 31 of 61

Version: 1.0, Dated 12 September 2019

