7.1.2 Recording of adverse events

All adverse events of any patient during the course of the trial will be reported in the case report form, and the investigator will give his or her opinion as to the relationship of the adverse event to trial drug treatment (i.e., whether the event is related or unrelated to trial drug administration). If the adverse event is serious, it should be reported immediately to Sponsor. Other untoward events occurring in the framework of a clinical trial are also to be recorded as AEs (i.e., AEs that occur prior to initiation of study drug that are related to a protocol-mandated intervention, including invasive procedures such as biopsies, medication washout, or no treatment run-in).

All AEs regardless of seriousness or relationship to Tenalisib, spanning from the informed consent drug until 30 calendar days after the last dose of study drug, discontinuation or completion of protocol-specific treatment as defined by the protocol for that patient, are to be recorded in the electronic Case Record Form (CRF).

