7.3.2 Serious adverse event reporting by Investigators

It is important to distinguish between "serious" and "severe" adverse events, as the terms are not synonymous. Severity is a measure of intensity; however, an AE of severe intensity need not necessarily be considered serious. For example, nausea which persists for several hours may be considered severe nausea but may not be considered an SAE. On the other hand, a stroke which results in only a limited degree of disability may be considered only a mild stroke but would be considered an SAE. Severity and seriousness should be independently assessed when recording AEs on the CRF and SAEs on the SAE Report Form.

Adverse events classified by the treating investigator as **serious** require expeditious handling and reporting to sponsor in order to comply with regulatory requirements. Serious adverse events may occur at any time from the signing of the informed consent form through the 30-day follow-up period after the last dose of drug. Sponsor/sponsor representative must be notified of all SAEs, regardless of causality, within 1 day of the first knowledge of the event by the investigator.

CONFIDENTIAL Page 39 of 61

Version: 1.0, Dated 12 September 2019

To report an SAE, the SAE report form should be completed with the necessary information. All SAEs occurring from the signing of consent until 30 calendar days of last dose of study drug must be reported to the Sponsor as SAEs on the SAE Report and followed until resolution (with autopsy report if applicable).

Deaths and other SAEs occurring >30 calendar days after last dose of study drug that are deemed 'possibly' or 'probably' related to Tenalisib must be reported as SAEs on the SAE Report within 1 day of first knowledge of the event by the treating physician or research personnel (with an autopsy report if available). Deaths occurring >30 calendar days after last dose of study drug and not attributed to study drug (e.g., disease progression) need not be reported as SAEs, but simply captured on the appropriate CRF.

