9.3.3 Missing dates for Primary Diagnosis/Prior therapy

Partial Primary diagnosis and prior therapy dates will have imputation performed as explained below for the purposes of calculation of relativity to study medication.

- If only Day is missing, impute the day 1
- If Day and Month are missing, impute the Month as January and the Day as 1.
- If the year of primary diagnosis is missing or the date of primary diagnosis is completely missing, then no date will be imputed.

10. Statistical Analysis

Due to early closure of the study, the analysis proposed in the SAP is based on the available data at the time of study closure.

The safety endpoints will be listed and/or summarized. No inferential statistical analyses will be performed.

Unless otherwise stated, all statistical analyses will be performed using a two-sided hypothesis test at the overall 5% level of significance.

When count data are presented, the percentage will be suppressed when the count is zero in order to draw attention to the non-zero counts. A row denoted "Missing" will be included in count tabulations where necessary to account for dropouts and missing patients. Unless otherwise specified, the denominator for percentages will be the number of patients with a non-missing assessment in a given treatment group within the analysis population of interest.

All statistical analyses will be performed using SAS 9.4 or higher.

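### The C8D1 end-of-study rules conflict with the 30-day adverse event follow-up and can leave completers who do not roll over without a scheduled contact

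*Protocol*

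**What the plan says.** **The 30-day rule.** Protocol Section 6.9 opens with "All patients must be followed for adverse events for 30 calendar days after the last dose of study drug". The overview in Section 6.1 lists "End of Study (Day +30 from last dose", and Table 1 gives Day 197 for C8/EOT and Day 227 for EOS. Table 1 footnote 19 repeats the rule: "Patients should be followed for AEs for 30 calendar days after the last dose of study drug". Section 7.1.2 records AEs "until 30 calendar days after the last dose of study drug, discontinuation or completion of protocol-specific treatment as defined by the protocol for that patient". Section 7.3.2 says "All SAEs occurring from the signing of consent until 30 calendar days of last dose of study drug must be reported to the Sponsor". None of these has an exception for roll-over.

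**The C8D1 exception.** Later in Section 6.9: "Patients who will be considered for compassionate use study protocol will have EOS visit on C8D1". Section 6.8 uses the same trigger, being *considered*, to place the EOT assessment on C8D1. Footnote 18 of Table 1 uses another trigger, patients who *participate* in RP6530-1803, and exempts them only from the EOT assessment timing.

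**End of study.** Protocol Section 3.2 says "The study will end when all ongoing subjects have reached their third tumor assessment on Cycle 8/Day 1 (C8D1") or have discontinued. The synopsis, Section 3.6 and SAP Section 5 say the same.

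**The SAP.** The notes to SAP Section 5.1 and the opening of SAP Section 10 tie the analysis to what is in hand when the study completes or closes: "the analysis proposed in the SAP is based on the available data at the time of study closure". SAP Section 10.6.2 defines a TEAE by its start relative to first dose and gives no end to the window.

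**The concern.** Section 6.9 gives two instructions for the same patient. Being considered for RP6530-1803 is not the same as receiving drug there: Section 5.1 says a patient may be enrolled, and Sections 3.2 and 6.8 speak of an opportunity. A patient who finishes treatment, is considered, and then declines or is never dosed has EOS on C8D1, and nothing in the schedule then prompts a contact 30 days later.

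Separately, the study-level rule can be met while a completer's 30 days are still running. If the analysis uses data available at closure, the last completers who do not roll over may be analysed without that contact.

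Safety and tolerability is the first secondary objective, and AEs, Grade 3/4 AEs and SAEs are the safety endpoints. What is at stake is how complete those descriptive summaries are, and whether a reader can tell how long each patient was observed.

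**Working it through.** **1. Reproduce the schedule (Table 1).**
- C8D1 = 7 cycles × 28 days + 1 = Day 197, as stated.
- EOS = 197 + 30 = Day 227, as stated.
- 227 / 30.4375 = 7.46 months. This agrees with the 7.5 months of treatment and follow-up in the synopsis, so the planned timeline includes the 30 days.

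**2. Compare the end-of-study day by type of patient who reaches C8D1.**

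| Patient | 30-day rule (6.1, Table 1, 6.9 first sentence) | C8D1 wording in 6.9 | Study-end rule if last patient |
|---|---|---|---|
| Completes, not considered for RP6530-1803 | Day 227 | does not apply | Day 197 |
| Considered, never dosed in RP6530-1803 | Day 227 | Day 197 | Day 197 |
| Considered and dosed in RP6530-1803 | runs from a later last dose | Day 197 | Day 197 |

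The first two rows show the conflict. In the second, Section 6.9 itself yields both Day 227 and Day 197. In the first, the patient-level rule gives Day 227 while the study may end on Day 197. In the third, dosing goes on and the documents say the patient will be followed up, so the post-last-dose window has not opened at C8D1.

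One wrinkle affects the third row. Section 7.1.2 names completion of protocol treatment beside last dose as a reference point, so a 30-day clock from C8D1 is a possible reading there too. The documents do not say which study would record those events.

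**3. Size per affected patient.** Follow-up at issue is 227 − 197 = 30 days. As a share of the planned span, 30 / 227 = 13.2%.

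**4. Total size.** With k affected patients, the days at issue are 30k. The documents do not give k. It may be 0. The SAP reports 21 enrolled, so the arithmetic ceiling is 21 × 30 = 630 patient-days. That would need every patient to reach C8D1 and none to be dosed in RP6530-1803, so it is a bound and not an estimate.

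**5. Effect on the primary analysis.** None. ORR rests on assessments up to C8D1 or EOT. The two-stage rule also reproduces: stopping at 8 or fewer of 20, and rejecting at 31 or more of 61, gives alpha 0.049 at 40% and power 0.904 at 60%. Moving the EOS contact changes neither.

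**6. A related mark in Table 1.** The C8/EOT column carries both treatment and dispensing marks, whereas Section 6.8 has treatment in this study running until C8D1. The 30-day clock starts at the last dose, so these entries need to agree before Day 227 is well defined.

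**The case against.** The strongest reply is that the C8D1 sentence is a hand-over clause. A patient entering RP6530-1803 keeps taking Tenalisib and is followed there, so no post-treatment window has been cut short. This stands for patients who do roll over. A reader might infer that safety data on the longest-treated patients are lost, or that AE and SAE incidence is understated. The documents do not support that. They say nothing on how ongoing AEs pass between the studies or whether later events return to this database, and the RP6530-1803 protocol is not available here. Silence on the transfer does not show that events go uncollected.

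A second reply is that the EOS visit date and the reporting window are different things. Sections 7.1.2 and 7.3.2 still oblige sites to record AEs and report SAEs for 30 days, and Section 6.9 follows related events to resolution or stabilization. This stands in part. The duty remains for a patient who is considered but never dosed, but the visit that would detect new events is missing from the schedule.

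A third is that the SAP excludes nothing: its TEAE definition has no end date, and its closure wording explains the early stop. That is also fair. The SAP does not set a cut before the 30-day contact, but it does not place the cut after it either.

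Two further inferences should be resisted. EOS is not set at C8D1 for everyone; the general rule is last dose plus 30 days. Nor is follow-up shown to depend on response, since patients with stable disease also continue and may roll over. Any difference would go with roll-over status.

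**Conclusion.** The concern holds in a limited form. Section 6.9 contradicts itself and Section 6.1, Table 1 with footnote 19, and Sections 7.1.2 and 7.3.2. It also uses a different trigger from footnote 18. The study-end rule can fall at Day 197, before the Day 227 contact.

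The gap covers two groups: patients considered for RP6530-1803 but never dosed there, and completers who do not roll over and whose 30 days run past study end. For each, up to 30 of 227 days (13%) may lack a scheduled contact within the study. This assumes that sites follow the C8D1 wording literally and that the data cut follows the study-end rule. For patients who roll over, only the description of the AE hand-over is missing.

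Descriptive safety may therefore be incomplete, in a single-arm trial that stopped after Stage 1 and plans no inferential safety analysis. No missed event has been shown.

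**What to change.** Reconcile the passages under the protocol's own 30-day rule:

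- **Sections 6.8 and 6.9, footnote 18.** Use one trigger. Apply the C8D1 exception only to patients who receive a first dose under RP6530-1803. Everyone else has the 30-day contact already planned, for which telephone is allowed.
- **Synopsis, Sections 3.2 and 3.6, SAP Section 5.** Define end of study as the last patient's EOS contact.
- **SAP Sections 5.1, 10 and 10.6.2.** Place the safety data cut after the last 30-day contact. State where the TEAE window ends; for roll-over patients, that is the first dose under RP6530-1803. Say how AEs ongoing at that point are handed over.
- **Table 1.** Reconcile the treatment and dispensing marks at C8/EOT with treatment in this study ending at C8D1.

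Because Stage 2 will not be run, the SAP changes are the ones that still bear on the report. The patient-visit listing in SAP Section 12 could also show how many patients had EOS on C8D1 without being dosed in RP6530-1803, which would replace the unknown k with a count.

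The cost is wording, plus database lock up to about 30 days later. Sample size, alpha and power do not change.
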